## 1. PURPOSE OF THE STUDY

---

### a. Brief Summary

The diagnosis of major depression relies on patient reports, and two patients with the same diagnosis might share only one symptom. Thus, a single mechanism is unlikely to underlie a broad descriptive diagnosis such as major depression. Our approach is anchored by a neural circuit taxonomy that proposes distinct biotypes of depression derived from functional magnetic resonance imaging (fMRI)(Williams et al., 2016). In this study, we aim to target a putative type of major depression that arises from dysfunction in cognitive control neural circuitry with a drug called guanfacine.

---

### b. Objectives

The proposed study addresses a public health need, generated by the burden of illness from depression. Major depressive disorder (MDD) is a prevalent and disabling condition; the 1-year prevalence is approximately 17%, and lifetime prevalence is as high as 25% globally. Only a subset of individuals with depression reach symptomatic remission after adequate treatment with first-line antidepressant medication treatment, estimated at approximately 30-40%. Dysfunction in a large-scale neural circuit alternatively called the executive or cognitive control circuit is associated with cognitive symptoms, including executive dysfunction and difficulty concentrating. These are core symptoms of depression and among the most frequently reported untreated symptoms of MDD.

Cognition is central to clinical and quality of life outcomes in depression. Research has repeatedly shown that cognitive impairments are not effectively treated by antidepressant medications. A significant proportion of MDD patients continue to experience debilitating cognitive symptoms even after attaining remission of mood symptoms with antidepressant treatment. These cognitive impairments are implicated in depression relapse and associated morbidity, highlighting the need for novel treatments that improve cognitive dysfunction in depression.

Guanfacine immediate release (Brand Name: Tenex) is an FDA-approved medication for hypertension and is used off-label for ADHD. The extended-release formulation is FDA-approved for treating ADHD in children and adolescents. In this study, we aim to

determine whether guanfacine immediate release (referred to hereafter as guanfacine or GIR) preferentially increases activation in a key node (dorsolateral prefrontal cortex, dLPFC) of the cognitive control circuit in participants with MDD, low baseline activation in this node, and cognitive deficits as compared to placebo as well as guanfacine in MDD participants with high baseline activation. Furthermore, we aim to determine whether change in dLPFC activation is correlated with changes in cognition. If our hypotheses are correct, baseline activation in the dLPFC may serve as a mechanistic neural target for treatment of symptoms with guanfacine in a subgroup of patients with MDD as well as a baseline predictor of response. Thus, this study will move us toward a more personalized and brain-based model of depression.

We will use GIR as it has been used more extensively than extended-release guanfacine in adult populations with cognitive deficits and has been shown to alter task-evoked dLPFC activation.

---

**c. Rationale for Research in Humans**

The purpose of the study is to specifically assess how guanfacine affects activation in the dLPFC and whether its effects correlate with change in cognitive function, including working memory, attention, and executive function in humans. It is difficult to identify a proxy for the spectrum of cognitive impairments in depression using animal models. Additionally, much of our knowledge of brain connectivity comes from studies in nonhuman primates and rodents. The human brain, however, is more complex in its architectonics than those of non-human primates or rodents. There is significant variability among humans in regard to brain anatomy and connectivity, as ascertained with fMRI. As such, understanding neural circuits of the human brain requires its direct study.

---

**2. STUDY PROCEDURES**

---

**a. Procedures**

1. Recruitment and screening: Participants experiencing depressive symptoms and not taking any psychiatric medications as determined by a 5 half-life wash out period will be recruited from the community, including students and employees at Stanford. Recruitment will come primarily from Facebook ads, which will use only IRB approved material. A flyer will also be physically posted on boards in public locations in order to include a variety of sources for the study.
2. Individuals will need to participate in 3 screening visits in order to enroll in the study. During the first visit, participants will review informed consent, be administered a clinical interview, and be sent instructions for completing cognitive testing at home.
3. If eligibility after this initial screening visit, the second visit will be a medical screen in order to ensure participants are safe to take GIR and will include standard blood tests, medical history, vitals, and a urine drug test.
4. If the participant meets medical and cognitive criteria, functional magnetic resonance imaging (fMRI) scans will be undertaken at another study visit at The Stanford Center for Cognitive and Neurobiological Imaging (CNI). Using a participant's task-evoked activity

in the dorsolateral prefrontal cortex (dLPFC) and performance on objective cognitive testing, we will apply thresholds using established healthy norms to select participants within the cognitive biotype+ group.

5. Participants will receive GIR for a period of 8 weeks sent to their place of residence from Mariner pharmacy.
6. Participants will be seen in-person or virtually by a study clinician at weeks 2, 4, 6, 8, and 10 and an appropriately trained clinical research coordinator at weeks 1, 3, 5, 7, and 9. All subjects will have an fMRI scan after 6-8 weeks of taking GIR. During in-person visits and virtual monitoring, we will assess participants for the following: changes to symptoms, function, and suicidality, adherence to GIR, changes to concomitant medication(s), adverse events (AEs), birth control usage compliance, likelihood of pregnancy (female participants of childbearing potential), and vital signs if appropriate.
7. If participants wish to continue GIR and their psychiatrist or PCP is willing to prescribe this, they will continue with their current dose for weeks 9 and 10. If they prefer to stop taking GIR and/or they do not have a provider who is willing to continue GIR, the participant will be tapered off the medication.

---

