**h. Eligibility Criteria**

**i. Inclusion Criteria**

- 18-69 years of age (inclusive)

- Go-NoGo fMRI task-evoked dLPFC  $\leq$  - 0.5 SD below the mean of normative sample
- Behavioral cognitive control performance  $\leq$  - 0.5 SD below the mean of normative sample on a Maze, Digit Span, and/or Verbal Interference (Stroop) task administered using WebNeuro
- Score  $\geq$  14 on the 17-item Hamilton Depression Rating Scale-17 (HDRS-17)
- Meets DSM-5 diagnostic criteria for current, past, or recurrent nonpsychotic major depressive disorder established by MINI Plus
- Medication naïve to guanfacine
- Fluent and literate in English, and show non-impaired intellectual abilities to ensure adequate comprehension of the task instructions
- Written, informed consent
- fMRI scanning eligibility, including no evidence of any form of metal embedded in the body (e.g., metal wires, nuts, bolts, screws, plates, sutures), as these produce artifacts when brain imaging. All potential subjects will need to successfully complete the screening forms at the Stanford Center for Cognitive and Neurobiological Imaging (CNI).

ii. Exclusion Criteria

- Presence of suicidal ideations representing imminent risk, defined by a score of  $>$  8 on the MINI-Plus, or by clinician judgement
- Lifetime history of medical illness or injury that may compromise cognitive functioning or interfere with assessments as deemed by the study physician (such as neurological disorders such as seizures or stroke, Parkinson's disease, dementia, or traumatic brain injury)
- Severe impediment to vision, hearing, and/or hand movement likely to interfere with ability to complete the assessments, or are unable and/or unlikely to follow the study protocols
- Pregnant, breastfeeding or unwilling or unable to use adequate birth control throughout the study
- Loss of consciousness for  $>$  10 minutes during lifetime
- Any contraindication to being scanned in the 3.0T scanner at the CNI such as having a pacemaker or implanted device that has not been cleared for scanning at 3.0 Tesla
- Previous or current DSM-5 bipolar disorder (I, II, not otherwise specified) or psychosis
- Meets criteria for DSM-5 alcohol or substance use disorder within the last 12 months
- Meets criteria for current DSM-5 PTSD, OCD, or eating disorder
- Concurrent participation in other intervention or treatment studies

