- Current use of psychotropic medications. If their usual treating physician is supportive, participants who are currently on psychotropics that can be safely tapered may be tapered off to participate but participant must wait 5 half-lives prior to first scan
- Current use of a strong CYP3A4 inhibitor or inducer (macrolide/ketolide antibiotics [clarithromycin, telithromycin], azole antifungals [itraconazole,

ketoconazole, posaconazole, voriconazole], protease inhibitors [atazanavir, darunavir, indinavir, lopinavir, nelfinavir, ombitasvir, paritaprevir, ritonavir, saquinavir], ceritinib, cobicistat, and idealisib), or inducer (apalutamide, carbamazepine, enzalutamide, fosphenytoin, lumacaftor, lumacaftor-ivacaftor, mitotane, phenobarbital, phenytoin, primidone, rifampin)

- Hypotension as defined by SBP  $\leq$  90 and/or DBP  $\leq$  60 on 2 of 3 separate measurements at least 5 minutes apart, bradycardia as defined by HR  $\leq$  55 on 2 of 3 separate measurements at least 5 minutes apart
- General medical condition, disease, or neurological disorder as reported by participant or found on in-person screenings that is deemed by the study physicians to be unsafe for GIR treatment, including kidney or liver impairment that is deemed to be unsafe, EKG abnormalities that are deemed to be unsafe, or cardiovascular disease deemed to be unsafe.
- History of sudden cardiac death in first degree relatives
- Positive drug screen for any substance deemed by the study physician to be unsafe for use with GIR in combination with other information obtained during screening

---

i. **Screening Procedures**

Participants will complete an online eligibility survey, provide informed consent, and attend two screening visits. Screenings include clinical interviews, medical history, cognitive testing, and functional MRI scans to assess dLPFC activation.

---

j. **Participation in Multiple Protocols**

Participants will first be screened via an online REDCap survey in order to determine initial eligibility. Once participants have completed the survey and have been determined eligible, they will continue to an in-person visit where consenting will take place and further screening procedures will be completed.

Participants will be screened for assessment of inclusion and exclusion criteria at the in-person baseline visit. We will ensure that consent is obtained and enrollment completed before personal health information is collected.

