We also screen using the following physical and laboratory tests:

a) **Physical Exam:**

- Participants will be asked to provide additional details of their medical history specifically relevant to the treatment contraindications (exclusion criteria). For standard monitoring, we will assess height, weight, vital signs, systems assessment, and general medical presentation during the physical exam.

b) **Laboratory Testing:**

- For standard monitoring, we undertake the following:
  - **Blood sample:** Analyzed for CBC, CMP, LFTs, TSH, and serum pregnancy test.
  - **Urine sample:** For urine drug screen.
  - **Electrocardiogram (EKG):** To assess cardiovascular health.

---

k. **Payments to Participants**

Research subjects will be offered [REDACTED] for the pretreatment fMRI session, self-report questionnaires, and cognitive assessments; and [REDACTED] for the subsequent MRI session at Week 8 of the treatment phase. Participants who complete the Monetary Incentive Delay (MID) task in the three MRI sessions will be offered an additional payment depending on their performance on the task, for a maximum total of [REDACTED] per session.

Participants will be compensated [REDACTED] for each of the 5 phone visits with completed questionnaires, [REDACTED] for the virtual or in-person physician check-ins at Weeks 2 and 8, and [REDACTED] for the physician check-ins at Weeks 4, 6, and 10.

---

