### **Secondary Outcomes**

For secondary outcomes, GLMs will include treatment as a within-subjects factor and a repeated measures factor for variables with multiple observations. Cognitive behavioral performance will comprise six test measures of cognitive control (Maze, Digit Span, Verbal Interference Color and Word, Switching of Attention, and GoNoGo), and quality of life, four domains (physical health, psychological health, social relationships, and environment) as measured by the World Health Organization Quality of Life – Brief (WHOQOL-BREF) Scale. Planned paired t-test contrasts will test for the effect of GIR on change in each set of individual secondary measures in each general linear model. The secondary measures of depression symptom severity (measured by the 17-item Hamilton Depression Rating Scale and Quick Inventory of Depressive Symptoms-Self Report), global satisfaction with life (assessed using the Satisfaction With Life Scale), and suicidality (measured by the Columbia-Suicide Severity Rating Scale Ideation Score) are exceptions that do not have repeated measures.

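### The week-8 HDRS-17 rating may be virtual although the baseline appears to be in person, and the pre/post analysis cannot separate a mode change from treatment

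*Protocol*

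**What the plan says.** **Baseline.** An HDRS-17 score of at least 14 is an inclusion criterion (Protocol 8.h). Protocol 2.a item 2 puts informed consent and a clinical interview at the first screening visit. Section 8.j says that, after the online survey, "they will continue to an in-person visit where consenting will take place and further screening procedures will be completed", and adds: "Participants will be screened for assessment of inclusion and exclusion criteria at the in-person baseline visit".

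**Week 8.** Section 2.g sets the endpoint for primary and secondary measures at 8 weeks. On the visits themselves, 2.a item 6 says "Participants will be seen in-person or virtually by a study clinician at weeks 2, 4, 6, 8, and 10", with symptoms, function and suicidality assessed in either mode. The payments section (8.k) repeats the choice for the endpoint visit: "virtual or in-person physician check-ins at Weeks 2 and 8".

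**Scan.** 2.a item 6 puts the follow-up scan after 6-8 weeks of treatment; 8.k describes it as a week-8 session.

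**Cognition.** At the first screening visit participants are to "be sent instructions for completing cognitive testing at home". The setting of the week-8 cognitive tests is not stated.

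**Analysis.** For secondary outcomes, "GLMs will include treatment as a within-subjects factor"; the SAP's primary-outcome section defines that factor as pre- versus post-treatment session. HDRS-17 is one of the secondary outcomes. The SAP has no between-arm comparison and no term for how a rating was obtained.

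**The concern.** A pre/post contrast attributes to treatment whatever differs systematically between the two occasions. If the HDRS-17 interview is held face to face at baseline and by video or telephone at week 8, the mode changes at the same time as the treatment factor. If virtual ratings run lower, the contrast overstates improvement; if they run higher, it understates it. A mixture of modes at week 8 also adds some variance to the change scores.

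The documents give no rule for choosing the week-8 mode and no requirement to match it to baseline or to record it. If it is not recorded, nothing can be done about it at analysis.

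What is at stake is the HDRS-17 result. The Columbia suicidality score could be touched too if it is interviewer-rated, which the documents do not say.

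**Working it through.** **Does the text permit a mode change?**

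1. 2.a item 2 places the clinical interview at the visit where consent is reviewed.
2. 8.j makes the consent visit in person.
3. HDRS-17 is needed for eligibility (8.h), so its baseline most naturally belongs to that interview. This step is an inference.
4. 2.a item 6 and 8.k each allow a virtual visit at week 8, the endpoint under 2.g.

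A change from in-person to virtual rating is therefore permitted, but not required.

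**How large could the effect be?** The plan gives no power, SD or effect size for HDRS-17, so there is no stated figure to reproduce. The calculation below is for scale only.

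Inputs from the documents: n = 25 (Protocol 8.a, planned enrollment) and a two-sided level of 0.05 (SAP).

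Assumed inputs: mode shift b = 1 point, in the same direction for everyone rated virtually; SD of change 6 (range 5 to 7); share of week-8 ratings that are virtual, s = 0.5 or 1; no true change apart from mode.

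Formulas:
- mean shift = b × s
- SD with mixed modes = √(SD² + b² × s × (1 − s))
- standardised shift d = mean shift / SD with mixed modes
- rejection rate = P(|T| > t), with T non-central t on n − 1 degrees of freedom and non-centrality d√n. For n = 25 the critical t is 2.064.

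Half virtual, SD 6: mean shift 0.5; SD √(36 + 0.25) = 6.02; d = 0.083; non-centrality 0.083 × 5 = 0.415; rejection rate 6.8%.

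All virtual, SD 6: mean shift 1; d = 1/6 = 0.167; non-centrality 0.833; rejection rate 12.6%.

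Rejection rates with n = 25:

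| Assumed shift | Share virtual | SD 5 | SD 6 | SD 7 |
|---|---|---|---|---|
| 0.5 point | half | 5.7% | 5.5% | 5.3% |
| 0.5 point | all | 7.7% | 6.9% | 6.4% |
| 1 point | half | 7.7% | 6.8% | 6.4% |
| 1 point | all | 16.1% | 12.6% | 10.5% |
| 2 points | half | 15.6% | 12.4% | 10.4% |
| 2 points | all | 48.4% | 36.0% | 27.9% |

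With n = 20, the 1-point, SD 6 rows become 6.4% (half) and 10.9% (all).

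For comparison, the effect detectable with 80% power at n = 25 is d = 0.58, or 0.58 × 6 = 3.5 points at SD 6. A 1-point shift is small beside that.

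**The case against.** Several counter-arguments have force.

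- **The in-person baseline is inferred.** Cognitive performance is also an eligibility criterion, yet it is tested at home, so the 8.j sentence cannot mean that every criterion is measured at that visit. That stands as a caution. The clinical interview is different, because 2.a item 2 ties it to the consent visit and 8.j makes that visit in person. The week-8 side is also partly inferred: 2.a item 6 speaks of changes to symptoms without naming HDRS-17.
- **The manual of procedures may already fix the mode.** Protocol 2.b item 5 says all procedures will be detailed there, and it is not among the documents. If it does, the protocol still needs to agree with it, since it now allows either mode.
- **The error rates rest on assumptions.** Reaching 13% requires every week-8 rating to be virtual and shifted the same way. This stands; the figures show scale, not an expected bias.
- **Mode is not the main weakness of an uncontrolled contrast.** Participants are selected on HDRS-17, so regression to the mean and expectancy can move the change score whatever the mode. This stands: fixing the mode removes one source of bias and does not by itself restore a 5% test. The protocol does refer to placebo and randomization, and a concurrent arm with the same mix of modes would largely cancel a mode effect, but the SAP makes no such comparison.

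Two stronger readings are tempting. A reader might infer that cognitive testing also changes setting, from home to supervised, because participants come on site for the scan. The documents do not support this: baseline testing is at home, nothing places the week-8 tests elsewhere, and repeating them at home is a natural reading. A reader might also infer that an in-person week-8 rating never needs an added visit. That fails for anyone scanned in week 6 or 7, which 2.a item 6 allows.

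**Conclusion.** The point holds in limited form. The protocol expressly allows a virtual endpoint visit, the baseline HDRS-17 is most plausibly rated in person, and the SAP's contrast has nothing to absorb a difference between the two. The mode change is permitted rather than planned, and its size and direction cannot be learned from the documents. Under the illustrative 1-point shift with SDs of 5 to 7 and n = 25, the rejection rate with no drug effect is 6.4% to 7.7% if half the week-8 ratings are virtual and 10.5% to 16.1% if all are.

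The scope is secondary and interviewer-rated: HDRS-17, and possibly the Columbia score. The primary outcome is measured in the scanner at both times, and the QIDS is self-reported. For WebNeuro there is only an unstated week-8 setting. This is a minor improvement to the plan, not a flaw that threatens its main result.

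**What to change.** 1. In Protocol 2.a item 6 and 8.k, state that the endpoint HDRS-17 is rated in the same mode as baseline, in person, and is combined with the on-site MRI session when that falls at week 8. The other clinician visits can keep either mode.
2. Where an in-person rating is not possible, allow a virtual one. The SAP uses listwise deletion, so a missed rating would drop the participant from the HDRS-17 analysis.
3. Record the mode of each HDRS-17 rating, and add to the SAP a sensitivity analysis restricted to participants rated in the same mode at both times. With at most 25 participants that subset may be small and selected, so it supports the main analysis and does not replace it.
4. As a clarification only, state that WebNeuro is repeated at home at week 8, as at baseline.

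The cost is a few sentences, one data field and one short analysis. The downside is small: participants scanned in week 6 or 7 may need an extra trip or the virtual fallback.

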**e. Alternative Procedures or Courses of Treatment**

There are currently no standard-of-care medications available that specifically target or treat cognitive impairment in depression. Initiation of antidepressant medication, particularly serotonin selective reuptake inhibitors (SSRIs), the first-line treatment for major depressive disorder, may be advantageous to participants. SSRIs typically take a minimum of 6-8 weeks once titrated to therapeutic dose to show therapeutic benefit with regard to symptoms. There are risks associated with SSRI treatment including medication side effects such as nausea, gastrointestinal side effects, increased anxiety, headaches, dizziness, fatigue, and a Black box warning of increasing risk of suicidal ideation in adolescence and young adulthood.

Electing to participate in the current study will delay initiating a trial of SSRI treatment by 6 weeks, but participants will then be able to continue with first-line therapy upon study completion. This information will be disclosed in the consenting process and form as standard-of-care drug.

---

**f. Will it be possible to continue the more (most) appropriate therapy for the participant(s) after the conclusion of the study?**

Upon completion of Week 8 of the treatment period, participants will have the choice of whether they would prefer to continue on the treatment or be tapered off the drug by the study MD during Weeks 9 and 10. To maintain the blind, participants who would like to continue treatment will be cross-titrated or down-titrated on their assigned medication (placebo or guanfacine) while simultaneously up-titrating on guanfacine.

Participants must have a physician willing to prescribe them guanfacine upon termination of the study and provide a note from their physician to the study clinician, or they will be tapered off the drug over the two-week safety phase. Upon request, a letter will be written to notify the physician of the participant's involvement in the study. This would facilitate the option for participants' usual care physician to continue treatment with GIR as part of their ongoing care of the participant after completion of the study.

---

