**g. Study Endpoint(s)**

The endpoint for primary and secondary measures will be 8 weeks after initiation of GIR or placebo, regardless of the study outcomes. Additional measures will be collected at the final endpoint of 10 weeks. If a subject reports a significant adverse event or worsening depression, the participant will be removed from the study. The study will not be terminated prematurely in the event that participants randomized to GIR have greater improvement than participants randomized to placebo.

---

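### The protocol gives two unreconciled medication instructions for weeks 9 and 10 to participants who choose to continue; they clearly conflict for anyone on placebo

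*Protocol*

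**What the plan says.** Two sections of the protocol cover what happens to study medication once the eight-week treatment period ends.

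- **Section 2.a, Procedures, item 7.** The instruction opens with its condition, "If participants wish to continue GIR and their psychiatrist or PCP is willing to prescribe this", and then says "they will continue with their current dose for weeks 9 and 10". Anyone who prefers to stop, or has no willing prescriber, is tapered off. The item mentions neither placebo, nor a blind, nor titration for those who continue.
- **Section 2.f, continuation of therapy after the study.** On completing week 8, participants choose whether to "continue on the treatment or be tapered off the drug by the study MD during Weeks 9 and 10". The rule for those who carry on begins "To maintain the blind, participants who would like to continue treatment" and says that they "will be cross-titrated or down-titrated on their assigned medication (placebo or guanfacine) while simultaneously up-titrating on guanfacine". It adds a prescriber condition, "Participants must have a physician willing to prescribe them guanfacine upon termination of the study", and asks for a note from that physician; failing this, the participant is tapered over a two-week safety phase.

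The surrounding text describes two different designs. Section 2.a, item 5 says "Participants will receive GIR for a period of 8 weeks", with no mention of a comparator, and the SAP's primary model is a pre/post comparison within subjects with no arm factor. By contrast, section 1.b (Objectives) names placebo as a comparator, and section 2.g (Study Endpoints) considers the case in which "participants randomized to GIR have greater improvement than participants randomized to placebo".

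**The concern.** Read one after the other, the two sections tell staff to do different things with the same participants in the same fortnight: leave the medication as it is, or change two supplies at once. If the trial has a placebo arm, which section is followed decides whether a placebo recipient who continues is exposed to guanfacine for the first time in weeks 9 and 10.

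That matters for participants and for interpretation. The protocol lists hypotension and bradycardia among guanfacine's side effects (section 9.a.iii) and reports blood pressure changes with it (section 9.c). A coordinator contact is scheduled at week 9 and a clinician visit at week 10, adverse events are recorded at both, and section 2.g calls for further measures at week 10. An event or a blood pressure reading from those visits cannot be interpreted unless it is clear whether guanfacine was being started, changed, held or not given.

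**Working it through.** No sample size, power or error-rate figure bears on this point, so the check is a comparison of the two texts, followed by a bound on the numbers.

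**1. Same participants?** Yes. Both sections address those who wish to continue, both require a willing prescriber, and both send everyone else to a taper. They agree about those who stop, so any conflict is confined to those who continue.

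**2. Same period?** Yes, by a short inference. Item 7 names weeks 9 and 10 outright. Section 2.f attaches those weeks by name only to the taper, but it presents continuing as the alternative at the same decision point (completion of week 8), and the only study period that follows is the two-week safety phase.

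**3. Same action?** This depends on what the participant is taking.

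| Taking at week 8 | Section 2.a, item 7 | Section 2.f | Compatible? |
|---|---|---|---|
| Placebo | Unchanged, so no guanfacine | Guanfacine started and raised | No |
| Guanfacine | Unchanged | Assigned supply titrated down, guanfacine titrated up; total dose not stated | Not determinable from the text |

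In the second row, a cross-titration could leave the total dose where it was, or could alter it. The dosing entry in section 6.b does not help: it gives the starting schedule and says nothing about weeks 9 and 10.

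**4. How many?** Let *p* be the proportion assigned to placebo and *c* the proportion of those who continue with a prescriber and a physician's note. With the planned enrolment of 25 in section 8.a:

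number in clear conflict = 25 × *p* × *c*

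The documents give neither *p* nor *c*. If there is no placebo arm, *p* = 0 and the result is 25 × 0 × *c* = 0. If there is one, some participants are on guanfacine, so *p* < 1 and the result is below 25. The figure of 25 is therefore a ceiling on those to whom the two instructions could apply, not an estimate of those whose treatment would differ.

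**5. Which data?** Section 2.g places the primary and secondary endpoints at week 8, and section 2.a puts the follow-up scan after 6 to 8 weeks of treatment. Both precede the conflict. The SAP defines no week-10 analysis. What remains is exposure, safety observations in weeks 9 and 10, and the week-10 measures.

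**The case against.** The strongest reply is that this is a symptom of a larger inconsistency. Item 7 belongs to text in which everyone takes guanfacine, as does the SAP; the titration sentence in section 2.f belongs to text describing a blinded, placebo-controlled trial. Once the sponsor says which trial is being run, most of the difficulty goes. This stands as an account of the likely cause. It does not remove the point: both sentences are current text, nothing marks either as superseded, and correcting the design statement in section 2.g or the SAP would not by itself amend item 7 or section 2.f.

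A second reply is that the instructions need not clash for someone already on guanfacine, since moving from one supply to another could preserve the dose. That stands. A reader might infer that the two instructions are mutually exclusive for every participant; the documents support this only for placebo recipients.

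A third is that little analytic weight rests on weeks 9 and 10. Exposure is already mixed then, because some taper while others continue; monitoring proceeds under either instruction; and no week-10 analysis is planned. This too stands, and it limits the consequence to safety and to interpretation of the extra measures.

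Finally, section 2.b says that procedures will be detailed in a manual which staff must follow. That manual is not among the documents. It may give a single instruction, so one cannot conclude that staff will in fact act inconsistently. It does not cure a protocol that says two things.

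**Conclusion.** The point holds in limited form. The two sections give unreconciled medication instructions for weeks 9 and 10 to participants who continue with a willing prescriber. They are incompatible for anyone on placebo. For anyone on guanfacine they are unreconciled, without a shown difference in dose.

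The number in clear conflict is unknown: zero if the trial has no placebo arm, and otherwise the placebo recipients who continue, fewer than 25. The conclusion assumes that section 2.f's rule for continuing participants applies to the two weeks after week 8, which its structure implies but does not state in so many words.

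Two stronger readings should be resisted. One might infer that all 25 participants face contradictory dosing; the documents do not show this under either design. One might also infer that the trial's main results are at risk; the primary and secondary endpoints are fixed at week 8, before the conflict arises. Nor do the documents establish which of the two instructions is the intended one. The matter should still be corrected, because it concerns what participants are given and the wording can be settled cheaply.

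**What to change.** Reconcile section 2.a, item 7 with section 2.f into one procedure for weeks 9 and 10, set it out once, and refer to it from the other place. The single text should say what happens to the assigned medication and to guanfacine for those who continue, and whether the total dose is meant to stay the same for someone already taking guanfacine.

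Make this change together with a clear statement of whether the trial has a placebo arm and a blind, and bring sections 1.b, 2.a, 2.f and 2.g and the SAP's primary model into line with it. Which procedure is right is for the investigators; this review takes no view.

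For the weeks 9-10 instruction, the cost is a protocol wording amendment, with the procedures manual checked against it. It requires no change to the sample size or to the week-8 analysis. Settling the design question may have wider consequences of its own, but those do not arise from this point.
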